Background: Despite proven benefits, the proportion of people with COPD who receive Pulmonary Rehabilitation (PR) is very small. The current model of a center-based PR program fails to address the needs of many patients with COPD. The most common patient barrier to attendance is travel to center-based programs, particularly for frail patients with more severe COPD who need transportation assistance. Home-based, unsupervised PR has been proposed as an alternative model to hospital-based programs and has been found to be safe and effective. In particular PR post-hospitalization has been reported as the most effective intervention to prevent a hospital readmission; however, the reality is that many times this is not a feasible intervention as only 4% of eligible individuals are able to adhere to PR after a hospital admission (for multiple reasons). While COPD is responsible for nearly 700,000 hospitalizations annually, many of these hospitalizations, which account for a large proportion of the annual direct medical costs of COPD, are potentially preventable readmissions.

Study Design and Methods

Methods:

Figure 1

Phase 1 (R61): A cohort of 10-15 patients will be recruited after a COPD-related hospitalization (COPD exacerbation or pneumonia) to use the home PR program system plus telephonic coaching for twelve weeks, and provide feedback through a qualitative study to refine the PR program system to be acceptable for the post-hospitalization period. Patients will be recruited until themes saturation (no more new feedback from patients).

We will use a natural language processing program to query the electronic medical records of Mayo Clinic Rochester to identify all patients presenting with COPD-related illness. In addition we will screen the patients admitted to the Chest Service (Domitilla 6B) of Saint Mary's Hospital. The study coordinator will receive the list of participants (with research authorization already processed through the natural language program) and will meet the patient in the hospital before they are discharged.

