During the consent process, the patient will have the opportunity to try the proposed home-based PR system in the hospital room, aiding in their confidence in their ability to use the system and the ease of the exercises. The study team will provide a step by step demonstration of the exercises (following the exercises on the computer tablet). The participant will be asked to rate their confidence to use the technology presented and their confidence (self-efficacy) to perform the home rehabilitation routine on a scale from 0 (no confidence) to 10

(great confidence). A rating of five or greater will be deemed an acceptable confidence level to participate in the study.

Each participant will be asked to define a particular place and time they can perform the home-based PR. The physical and mental environment is critical for the successful adoption of new behavior (PR). Participants will learn about the weekly calls with the coach to discuss their rehabilitation and monitored measures (steps, level of shortness of breath, well-being, and fatigue). They will then go over the daily answers to well-being questions (mood, breathlessness, and energy, as tested in the pilot study and shown in Fig.2; see participant software application section below). After performing the PR routine (to ensure safety and understanding) and reviewing the use of the monitors, a plan for a PR coach call, a week to 10 days after discharge. The participant will use the criterion activity monitor (Actigraph, Fig. 3) that will determine the baseline physical activity during the first week immediately after discharge to define a baseline physical activity. The coordinator will discuss the in-home activities with the participant to identify possible exercise-related fall hazards in the home environment.

[figure not shown]

Figure 2

Figure 3

Figure 4

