Participants are expected to engage in the home-based PR at least six days a week. The Garmin Vivofit™ activity monitor (Fig. 4) is to be worn at all times (battery lasts one year) to capture daily steps and the metabolic equivalent of tasks (METs) per day. The PR routine begins with a slow breathing awareness exercise, “pursed lips breathing,” followed by upper-extremity exercises (Fig. 2), then two walks (in the home or outside) for 6 minutes, and finishing with another slow and mindful pursed-lips breathing exercise. The exercise protocol lasts about 20 minutes, which is the amount of *daily dedicated exercise* time associated with a risk reduction in hospitalization and improved QOL^{22,23} and is recommended by current PR guidelines.¹³ The proposed protocol is also currently being used by the PI of this proposal in a prospective COPD trial (R01 CA163293) in addition to the work cited in the preliminary data (R44 HL114162). The PR coach will contact by phone or mail the primary care, or referring, provider before initiating the PR program to introduce the provider to the study, as well as to coordinate and develop a strategy in case of a COPD exacerbation (a common cause of PR abandonment).

The proposed home-based PR system (Fig.1) consists of three commercial devices and two software applications. The devices are a Garmin Vivofit™ (AM), a Nonin 3150 WristOx2® Pulse Oximeter (PO), and a 7”

Android™ tablet with 3G/4G cellular service (Verizon). The AM and PO wirelessly communicate with the tablet

via Bluetooth. During the upper extremity exercise routine and walks, the PO measures the participants' heart rate (HR) and oxygen saturation (SpO2). Near the end of the day, the tablets periodically sound a musical alarm and display a short health status questionnaire (Fig. 2) asking participants to rate their well-being,24 ease of breathing, and energy level. At night, the tablets securely transmit the device data and well-being questionnaire answers to a remote Web server, which securely stores the data and generates reports. Health coaches call the participants weekly to discuss their progress in PR and SM (see below).

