Participant software application (tablet): When the participant turns on the Android™ tablet, the application logs in, and the participant accesses to the main screen (Fig. 5). To initiate one of these activities, the user selects the corresponding action from the “To-Do” column. Selecting “Exercise” from the “To-Do” column initiates a video guiding the user through the PR exercises (Fig. 6). Similarly, selecting “Walk” from the “To-Do” column starts a 6-minute countdown once the application detects that the participant has initiated walking. Before displaying the exercise and walking videos the application verifies that the participant is wearing the AM and PO to assure measure and compliance (during exercise an increase in heart rate is expected). When the participant finishes the selected activity, it appears in the “Done” column. The application provides instructions before and between each activity. Patients are asked to follow the videos in all PR sessions to maintain a minimal and equal “dose” of PR for all participants. The oximeter data during exercise is used as a measure of adherence and exercise time.

[figure not shown]

Figure 5

[figure not shown]

Figure 6

The “my journey” screen (Fig.7) plots historical data, allowing participants to see trends as in the pilot study.

[figure not shown]

Figure 7

From this screen, users can view daily steps, average heart rate, SpO2, and questionnaire answers. The user also can select the historical window (e.g., last week, last month, last quarter).

Coaching PR Calls (weeks 1-12) content for PR

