feedback plus SM: After the hospital and consenting visit, coaching calls will occur weekly for twelve weeks following this protocol: (1) Listen to the participant’s journey. (2) Provide feedback of the PR process at home based on the feedback from the coach application. Sessions will generate dialogue by listening to “change participant’s comments on anticipated activities. (3) If problems arise, resist the urge to attempt to solve the participant’s problems and barriers. (4) Listen carefully and kindly (ambivalence from the participant in changing their behavior). (5) Discuss how behaviors connect to the participant’s values and strengths. (6) Collaborate in setting goal(s) for the following week. A goal can be anything the patient wants to discuss even beyond PR (like smoking cessation, vaccinations, weight loss, etc.) (7) Discuss the process of action planning: elicit the participant’s preferences. (8) Elicit the participant’s choice; do not assign goals, and use the participant’s language to describe the goal. (9) Assess confidence for goal completion, reaffirm commitment to the action plan, and express optimism. (10) Thank the participant and plan the next call. (11) All calls will be recorded to ensure **fidelity** and **compliance** with the protocol and MI principles (10% of all calls will be reviewed).

Health Coach Software Application: The health coach software application provides three types of reports. The overview report (Fig. 8) allows health coaches to succinctly ascertain the status of their participants and flag anyone who may be experiencing problems. The health coach may select a participant from the overview to display the trend report (Fig. 9). The trend report allows the health coach to review the participant’s progress between weekly health coaching sessions. Finally, the health coach may select a day from the trend report to display a detailed report (figure 10).

Subjects		Alerts	Messages	Display			
Subject ID	Activity Monitor		Exercise and Walking			Check-In Questionnaire	
	Synchronized	Ave Step Count	Performed	Pulse Ox	Ave Duration	Answered	Concerns
pr10001	3 Days Ago	1402	2 Days Ago	●	4.4	2 Days Ago	●
pr10002	4 Days Ago	7900	5 Days Ago	●	8.4	5 Days Ago	
pr10003	Yesterday	10200	7+ Days Ago		0.0	7+ Days Ago	
pr10004	7+ Days Ago	0	7+ Days Ago		0.0	7+ Days Ago	
pr10005	5 Days Ago	0	7+ Days Ago		0.0	7+ Days Ago	
pr10006							
pr10007	Yesterday	9733	Yesterday	●	17.2	Yesterday	

[figure not shown]

Figure 8

Figure 9

Figure 10

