The primary endpoint of this study will be the rate of adherence compared between the two groups. Secondary endpoints include rates of COPD related hospitalization or death, activity levels as measured by the average number of steps per day, and the CRQ scales of dyspnea, fatigue, emotional function, physical, mastery, and the total score. Differences between groups will be compared with Fisher’s exact tests for proportions and ttests for continuous endpoints. These analyses will be supplemented with logistic regression models and linear models to compare groups after adjusting for confounding factors.

One hundred and forty-four patients will be entered on this study (72 per arm). After adjusting for multiple comparisons, this sample size will provide at least 80% power to detect a difference in the rates of adherence of 26% in the control group to 50% in the intervention group. This sample size will also provide at least 80% power for detecting a 50% reduction in hospitalization/death rates (from 50% in the control group at 6

months to 25% in the intervention group at 6 months), a difference of 1000 steps at 3 months (assuming a standard deviation [SD] of 2,000 steps), and a 0.5 difference in CRQ summary scores at 3 months (assuming an SD of 1.0). The sample size will be increased to 150 (75 per arm) to account for a 5% drop out rate.

Outcomes for the Phase 2 Randomized study

Aim 3a: Adherence will be our primary outcome

Overview: The reported adherence for PR after a hospitalization is 4% and in the best case scenario (free PR and free transportation like in the UK) is 10%. From our preliminary data, now in press (Respiratory Care), we found an adherence of >80% to the proposed system in outpatients with COPD. We hypothesize the adherence to a complete home-based PR program by post-hospitalized patients will be around 50%, and the adherence to the conventional hospital-based PR program to be 25% (due to our strong efforts to encourage people attend) will consider a complete PR when 75% of the expected PR visits are completed. We will compute the degree of completion of conventional PR from our electronic health record (EHR). The home-based PR compliance will be assessed by the entries of the PR coach in REDCap.

Aim 3b: CRQ Physical and Emotional Summary scores post PR

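### Primary endpoint: Aim 3a scores both arms from weaker or less complete records than the trial already collects, and does not fix the count to which the 75% rule applies

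*Combined protocol and SAP*

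**What the plan says.** **Rule.** Under Aim 3a the investigators "will consider a complete PR when 75% of the expected PR visits are completed". No count of expected visits is given for either arm.

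**Home arm, source.** Aim 3a states: "The home-based PR compliance will be assessed by the entries of the PR coach in REDCap". The section on the participant software application says of the same arm: "The oximeter data during exercise is used as a measure of adherence and exercise time". Study Design and Methods adds that the tablets send device data to a server each night.

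**Home arm, schedule.** Study Design and Methods says: "Participants are expected to engage in the home-based PR at least six days a week". The pilot cohort is "to use the home PR program system plus telephonic coaching for twelve weeks", and the coaching section says "coaching calls will occur weekly for twelve weeks". Phase 3 (R33) carries the home procedures into the trial. The ActiGraph "will determine the baseline physical activity during the first week immediately after discharge"; nothing says whether sessions in that week count.

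**Control arm.** Aim 3a takes the degree of completion from the institution's own EHR. The section on the conventional PR group has patients referred to their nearest program. Phase 2 (R61) has controls sign a release so that the study can obtain their rehabilitation records, and ties mileage payment to records confirming attendance. Aim 3a does not mention those records.

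**The concern.** The endpoint is a proportion reached or not reached, so it depends on who counts the sessions and what they are divided by. Both named sources invite question.

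In the home arm the scorer is the person who delivers the intervention and knows the assignment, while a more objective log exists. In contrast, Aim 3d assigns the utilization calls, which support a secondary outcome, to a blinded coordinator.

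In the control arm an internal record is asked to register attendance that may happen elsewhere. The plan knows that this kind of loss occurs: Aim 3d adds telephone calls to catch admissions outside the system, and the cost-effectiveness section concedes that use outside the network is not captured. The primary endpoint has no matching safeguard.

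Generous coach entries and missed control visits would both act in favor of home rehabilitation, so they would add up. An unfixed denominator has no set direction, but it leaves a choice that could be made after data are seen.

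**Working it through.** **1. The plan's own figure.** Inputs from Statistical Analysis and Power: 26% control, 50% home, 80% power. Two-sided 5% is stated for the t-tests and assumed for Fisher's test. (The parallel Data Analysis Plan text gives 6% for controls and Aim 3a gives 25%; 26% is used here.)

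- Uncorrected: n₀ = [1.960·√(2·0.38·0.62) + 0.842·√(0.26·0.74 + 0.50·0.50)]² / 0.24² = (1.345 + 0.560)² / 0.0576 ≈ 63.0, so 64 per arm.
- Continuity-corrected: n = (n₀/4)·[1 + √(1 + 4/(n₀·0.24))]² ≈ 15.75 × 4.51 ≈ 71.1, so 72 per arm, as stated.
- Exact Fisher power at 72 per arm, summing the binomial probabilities of all tables with p ≤ 0.05: 80.7%.

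The sample size reproduces, without any multiplicity adjustment. The problem lies in the endpoint, not in N.

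**2. Control capture.** Recorded rate = true rate × share of completers captured. The documents give no capture share, so it is an assumption, shown as a range. Fisher power at 72 per arm:

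| Share captured | Recorded control rate | Home 40% | Home 50% |
|---|---|---|---|
| 100% | 26.0% | 36.5% | 80.7% |
| 90% | 0.90 × 26% = 23.4% | 50.7% | 89.0% |
| 75% | 0.75 × 26% = 19.5% | 72.2% | 96.5% |

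The apparent gain is false: at 75% capture a true difference of 14 points (40 − 26) is recorded as 20.5 points (40 − 19.5). If both arms truly stood at 26%, the chance of a significant result would rise from 3.2% to 11.2%.

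**3. Coach entries.** Recorded rate = true × (1 − missed) + (1 − true) × wrongly credited. Error rates are assumed; true home completion is set at 45%.

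- None missed, 10% of non-completers credited: 0.45 + 0.55 × 0.10 = 50.5%.
- None missed, 20% credited: 0.45 + 0.55 × 0.20 = 56.0%.
- 10% missed, 10% credited: 0.405 + 0.055 = 46.0%.
- 10% missed, none credited: 40.5%.

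The direction depends on the kind of error, and the documents give no information on either kind.

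**4. Denominator.**

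- Home, six days for 12 weeks: 6 × 12 = 72, and 0.75 × 72 = 54 sessions.
- Home, first week excluded: 6 × 11 = 66, and 0.75 × 66 = 49.5, so 50 sessions.
- Home, daily (because six days is a minimum): 7 × 12 = 84, and 0.75 × 84 = 63 sessions.
- Control: no number, frequency or length of center visits is given, so no threshold can be computed.

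**The case against.** **Home denominator.** Six days a week for twelve weeks makes 72 the natural reading, and the word expected appears both in the schedule and in the endpoint rule. Reading visits as the 12 coach calls is strained, because the calls are coaching about rehabilitation rather than sessions. This stands: the home count is implied and only needs to be fixed.

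**Never-starters.** Zero visits is below 75% of any positive number, the hypothesized 25% control rate plainly includes non-attenders, and the missing-data section keeps all randomized subjects. This also stands. The rule should be written down, but its absence is missing detail.

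**Sources.** A reader might infer that the two statements on home adherence contradict each other. They need not: the coach's application displays exercise performed, pulse-oximetry status and average duration, so the entries may be transcribed from device data. Equally, outside records may be filed in the EHR. Neither step is stated, so this softens the concern without removing it.

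**Bias.** A reader might infer that the contrast is shown to favor home rehabilitation. It is not: capture shares and coach error rates are unknown.

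**Crossing 50%.** A reader might also infer that the definition alone moves home adherence across the planned 50%. The documents do not support that.

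- They contain no session distribution. With mean completion assumed at 60–67% (beta-binomial), the readings with some textual support give 28–39% (54 of 72), 38–50% (50 sessions, 72 opportunities kept) and 28–39% (63 of 84). Even 9 of 12 calls gives 37–47%.
- Easier thresholds that exceed 50%, such as three or five sessions a week, appear nowhere in the plan.
- Setting the 54-session rate at exactly 50% makes any easier or harder rule fall on either side by construction.
- The 50% is a planning rate, not a success boundary.

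**Conclusion.** The concern holds for the data sources and, as a lesser matter, for the unstated denominators. The sole primary endpoint is scored in one arm by the unblinded person delivering it, with no statement that the entries come from the devices. In the other arm it is scored from a record that, read literally, can miss patients who completed rehabilitation elsewhere. Better sources for both arms are already collected.

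The loss of control completers has a clear direction if it occurs, since it can only lower the recorded control rate. Its size rests wholly on the assumed capture share: at 75%, it would roughly double the power against 40% home adherence with no true change. The effect of coach scoring could go either way. The planned 72 per arm is sound on its own inputs. The finding is therefore an avoidable risk to the credibility of the primary comparison.

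**What to change.** Amend Aim 3a before any between-arm look at adherence:

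- **Home source:** score from tablet and oximeter session records, and state what constitutes a recorded session. Keep coach entries as a cross-check and as the documented fallback when a device fails to record or synchronize.
- **Home denominator:** state it from the protocol's own schedule, and say whether the first week after discharge counts.
- **Control source:** the EHR plus the released rehabilitation records.
- **Control denominator:** the number of visits in the attended program's own prescription.
- **Analysis set:** keep all randomized patients in the denominator, with those who never start counted as not adherent in either arm.

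The cost is protocol wording and some abstraction work. Device data are already uploaded, rehabilitation records are already requested, and N stays the same: 50% against 26% still gives 80.7% Fisher power at 72 per arm. There are two downsides. Home adherence may look lower than under coach entries, and without the fallback rule a device failure would be scored as non-adherence.

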While participant monitoring does not occur in real time, any significant physiologic abnormality measured during rehabilitation and transmitted to the server (O₂ saturation less than 80% or heart rate greater than 140 or less than 40 beats per minute) prompts a message to the coach to call the participant to investigate the event. The PI also is alerted within 24 hours by text message if a physiologic abnormality is measured to ensure the appropriate response. In R44HL114162-03 Home-Based Health Management of COPD Patients, the remote rehabilitation and health coaching system has been pilot tested together and found feasible, actionable, and acceptable. After the pilot is completed, a qualitative study will be done to identify areas of deficits to be changed and then adapted for the second phase of the study, a randomized control trial.

Phase 2 (R61): Mayo Clinic Rochester and Jacksonville Fl will participate in this Phase. Phase 2 will take part in year 2 of the study. After the study has been refined in Phase 1, thirty (30) participants (of the planned 150 subjects) will be recruited and randomized to one of two to the home-based PR or referred to conventional PR (standard of care). After the 30 subjects are enrolled, the study staff will review the feasibility, informing the team about accrual and outcome completion rate (questionnaires and activity monitors). This will allow the study team to forecast a complete and informative study for the R33.

The participants randomized to control/conventional care will be offered mileage reimbursement to and from a pulmonary rehab center. The mileage rate used will be the current IRS standard rate (57.5 cents per mile in 2020). The study will pay mileage up to a total of \$500. Study staff will use MapQuest to determine the miles from participants residence to the rehab center. The participants will be asked to sign an Authorization to Release Protected Health Information-Research in order to obtain Pulmonary Rehabilitation Records. Mileage will be paid monthly when possible, or when in receipt of the medical records confirming attendance.

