We plan to optimize the possibility of patients referred to conventional PR to attend by generating a dialogue about the importance of PR, facilitating the referral and then follow up with a call. This optimization initiative includes targeting the most prevalent problems that explain the current poor utilization of the traditional hospital-based PR after a hospitalization: (1) lack of a referral or strong recommendation from a physician (we plan to do a dedicated referral to the [patient indicating the nearest PR program and contact information including the proper referral order), and (2) inadequate follow-up or facilitation of enrollment after referral (we will communicate with the individuals two weeks after discharge to encourage PR program adherence). Finally, we acknowledge that many patients/caregivers will clearly express being unable to attend conventional PR and realize then that the control arm receive no active intervention. The latter is a significant problem in behavioral interventions that cannot be blinded. *To palliate that problem* and given that the project targets daily physical activity, we will provide every individual in the conventional PR group a Garmin Vivofit (Fig. 3), an activity monitor that has a large display and is easy to use so that they can monitor steps every day. We have ample experience on the use of this monitor in current pour proposal. This is the same monitor that individuals in the Home PR receive for daily use. The study does not cover standard of care treatment. **Home PR group: Proceedings will be as in the pilot study plus refinement (see R61, Phase 1 and 2).**

Recording of calls and qualitative interviews: All health coaching calls and the qualitative interviews will be recorded. The health coaching calls are recorded and the voice file saved on a secure research drive that only study team has access too. The files are saved under the participants subject number and the week of the call. The calls are randomly selected to be reviewed by the PI [name] and the Fidelity Officer, [name]. Dr.'s [name] and [name] will score the health coach using the MITI worksheet (attached, Appendix 1). The voicefiles will be deleted off of the research drive at the end of the study.

Resources:

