Aim 3d: COPD-related hospital readmission (COPD exacerbation or pneumonia as discharge diagnosis) at one month, three months and six months. They will be assessed by the EHR and also by Care Utilization Calls (a safety measure in case individuals are rehospitalized outside the Mayo system). The calls will occur every three months (to avoid recall bias), will use a scripted protocol as in a previous application, and will be conducted by a coordinator blinded to the intervention. Emergency Department (ED) visits and hospitalizations (all cause) will also be recorded.

Aim 4: CE analysis EuroQol Five Dimensions questionnaire

The EuroQol Five Dimensions questionnaire (EQ-5D) is a standardized instrument for measuring generic health status. The health status measured with EQ-5D is used for estimating preference weight for that health status, then, by combining the weight with time, a quality-adjusted life year (QALY) can be computed. QALYs gained its used as an outcome in the cost-utility analysis, which is a type of economic evaluation that compares the benefit and cost of healthcare programs or interventions. EQ-5D is one of the most commonly used generic health status measurements, and its good validity and reliability have been reported in various health conditions. It will be the tool to be used in the proposed cost-effectiveness analysis (CEA).

Secondary Outcomes

Self-Efficacy: The Mastery domain of the CRQ will be used to assess self-efficacy. The CRQ questions assessing self-efficacy are “In the last two weeks, how much of the time did you feel very confident and sure that you could deal with your illness?” and “How often during the last two weeks did you feel you had complete control of your breathing problems?”

Baseline Demographics and comorbidities: Baseline demographics to be collected include age, mMRC, FEV1, highest grade completed in school, marital status, gender, structural and functional social support,³³ race, steroid (prednisone) use in the three months before the study, comorbid conditions (Charlson Comorbidity Index), smoking status, and previous hospitalizations and ED visits.

Analyses

There are three *distinct* quantitative study hypotheses (inform different aspects of the process).

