Multivariate regression models will be employed to control for differences between study groups. Due to the highly skewed nature of healthcare costs, a generalized linear model incorporating a gamma distribution and log-link function will be used. The cost-effectiveness of the home PR intervention will be determined using the threshold of \$50,000/QALY. The 95% CI of the cost-effectiveness ratio will be calculated using nonparametric bootstrapping.

Healthcare utilization occurring at facilities outside of our network will not be captured. Sensitivity analysis of the cost-effectiveness will be performed based on residency status (local, regional, and distant).

Limitations: We acknowledge that comparing to completed regular PR would be ideal, however, given that the completion rate post-hospitalization is so low, accruing for such a study would be unrealistic. We strongly believe that the proposed design truly represents “a real world” study and the result from it would be applicable to the practicing clinicians and regulatory agencies and payers to further support alternative ways of PR (if our hypothesis is confirmed: increased adherence, decreased readmission and patients’ critical outcomes like daily physical activity and quality of living). We will put a dedicated effort to motivate individual to attend conventional PR if they are randomized to arm.

We will not know if the improvement in adherence is because of the home-based PR or health coaching. However, given that, only 4% complete conventional PR after a hospitalization, a meaningful improvement in adherence would not require much effort from the patients the home-based PR program.

R61 milestones (two years)

Year 1

1. Finalization of the protocol and the informed consent document
2. Development of the manual of operations and case report forms
3. Establishment of a Data and Safety Monitoring Board
4. Institutional Review Board approval of the trial
5. Pilot cohort of 10-15 patients to refine the intervention already developed for outpatients
6. Qualitative study and application of the necessary changes to the proposed Home PR

Year 2

Begin enrollment into the clinical trial to allow for an evaluation by the end of the R61 phase of early enrollment and the probability of completing the trial on time and budget. Target for year two will be to recruit 30 of 150 subjects planned for the whole study.

R33 milestones

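### Aim 3a takes control-arm completion from the institution's own EHR, although controls are referred to the nearest PR program; outside attendance records are not named as an endpoint source, and a control without records is not classified

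*Combined protocol and SAP*

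**What the plan says.** - **Endpoint.** Statistical Analysis and Power: "The primary endpoint of this study will be the rate of adherence compared between the two groups". Aim 3a counts a program as complete at 75% of expected visits.
- **Control source.** Aim 3a: "We will compute the degree of completion of conventional PR from our electronic health record (EHR"). No second source is named.
- **Home source.** Aim 3a uses the PR coach's entries in REDCap.
- **Where controls attend.** The section on referral to conventional PR describes a dedicated referral "indicating the nearest PR program and contact information including the proper referral order". It does not restrict attendance to the institution's own centers.
- **Access to records.** Phase 2 (R61): "The participants will be asked to sign an Authorization to Release Protected Health Information-Research in order to obtain Pulmonary Rehabilitation Records". The one use then stated for attendance records is payment: "Mileage will be paid monthly when possible, or when in receipt of the medical records confirming attendance". The Phase 3 (R33) text does not repeat the release.
- **Related gaps handled elsewhere.** For readmissions, Aim 3d adds telephone calls to the EHR as "a safety measure in case individuals are rehospitalized outside the Mayo system". The cost-effectiveness section says: "Healthcare utilization occurring at facilities outside of our network will not be captured", and adds: "Sensitivity analysis of the cost-effectiveness will be performed based on residency status (local, regional, and distant").
- **Missing data.** In the Analyses section, a missing month-3 measure is carried as no change from baseline. Assessment of Bias plans missing-not-at-random imputation for dropouts. Missing data describes a likelihood-based repeated-measures analysis.

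**The concern.** The control half of the primary endpoint is read from a record that need not contain the event. A control who attends a local program outside the institution can reach 75% of visits and leave no trace in its EHR. The home arm has a dedicated source, filled in by study staff during the weekly coaching. If absence from the EHR is read as non-completion, the error lowers only the control rate and so favors home PR.

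The utilization calls do not close the gap. As described under Health Care Utilization, they ask about doctor, emergency and hospital visits for breathing problems, and about antibiotics and prednisone, but not about PR sessions. Two things are at stake: the estimated difference in adherence, and, where true rates are close, the type I error of the primary test.

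**Working it through.** **1. Does the missing-data text classify a control without PR records?**

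- No change from baseline: completion has no baseline value, so the rule cannot be applied.
- Likelihood-based repeated measures: completion is a single binary outcome, not a repeated one.
- Missing-not-at-random imputation: this is limited to dropouts. A control can stay in the trial, return every questionnaire and still have no PR record.

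None of the three says whether such a control is a non-completer, missing or excluded.

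**2. The plan's own figure.** Inputs from Statistical Analysis and Power: 72 per arm, 26% vs 50%, Fisher's exact test. A two-sided 5% level is assumed; the plan states it only for the continuous outcomes. Power is the sum of Bin(x; 72, 0.26) × Bin(y; 72, 0.50) over all pairs (x, y) with Fisher p ≤ 0.05. The result is 80.7%, which agrees with the stated 80% or more.

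**3. Sensitivity to missed control completions.** Let p be the true completion rate, the same in both arms, L the share of control completions missed, and H the share of home completions missed. A missed completion is scored as non-completion. The observed rates are p(1 − L) for control and p(1 − H) for home. L and H are assumptions; the documents give neither. The table shows the probability that the Fisher test rejects, by the same enumeration.

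| True p | L | H = 0 | H = L/2 | H = L |
|---|---|---|---|---|
| 25% | 0 | 3.2% | 3.2% | 3.2% |
| 25% | 10% | 4.2% | 3.4% | 3.2% |
| 25% | 20% | 7.8% | 4.3% | 3.2% |
| 25% | 30% | 14.7% | 6.0% | 3.2% |
| 10% | 0 | 2.6% | 2.6% | 2.6% |
| 10% | 20% | 3.7% | 2.6% | 2.2% |
| 10% | 30% | 5.3% | 2.9% | 2.0% |
| 4% | 0 | 1.0% | 1.0% | 1.0% |
| 4% | 30% | 1.2% | 0.7% | 0.5% |

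The 25% is Aim 3a's hypothesis for the control arm. The 10% and 4% are the best-case and usual rates that Aim 3a reports for PR after hospitalization. At 25%, 72 × 0.25 = 18 controls complete, so L = 10/20/30% means 1.8/3.6/5.4 missed completers. With H = 0 and L = 30%, 14.6 of the 14.7 points are rejections in favor of home PR.

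**4. Effect on the estimate at Aim 3a's 25% vs 50%.**

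- H = 0, L = 20%: 0.50 − 0.25 × 0.80 = 0.30, against a true 0.25.
- H = 0, L = 30%: 0.50 − 0.25 × 0.70 = 0.325.
- H = L/2, L = 20%: 0.50 × 0.90 − 0.20 = 0.25, no distortion.
- H = L/2, L = 30%: 0.50 × 0.85 − 0.175 = 0.25, no distortion.

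**The case against.** The strongest answer is the planned release. Its stated purpose is to obtain PR records, under a research authorization, and it is not confined to payment. Mileage paid on confirmed attendance gives attending controls a reason to let the records through. A reader might infer from the EHR sentence, or from the cost-effectiveness statement about use outside the network, that outside attendance will simply be lost. The documents do not support that. The release puts most of the data within reach, and the cost-effectiveness statement concerns resource use, not the adherence endpoint.

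A reader might also infer that the primary comparison is biased. That requires that outside records never reach the institution's EHR, that absence is scored as non-completion, and that home entries are more complete. The plan states none of these, nor how many controls would attend elsewhere. The largest figure, 14.7%, combines 30% control loss, no home loss and equal 25% completion. If the planned 25% vs 50% is true, the undistorted test already rejects 84.2% of the time, so the qualitative conclusion would probably stand.

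These points limit the size of the problem and leave the gap open. Aim 3a names one source and does not mention the released records. Nothing says that they are filed in the EHR, or what happens when a control declines the release or a program does not reply. The imputation planned for dropouts overlaps with a sensitivity analysis of this kind but does not reach controls who remain in the trial.

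**Conclusion.** The point holds as a defect in the endpoint rule. It is not a demonstrated bias. As written, Aim 3a can count outside completers as non-completers, and any such error favors home PR unless home-arm entries are similarly incomplete. The size cannot be determined from the documents. It matters mainly if control completion is near the planned 25% and control records are clearly less complete than the coach entries. At 4–10% true completion no computed scenario exceeds 5.3%, and with equal loss in both arms there is no inflation. If the released records are obtained and used for all controls, the problem largely disappears. It should be fixed, and before outcomes are known, because choosing the source or the classification afterwards could change the primary result. Confidence is medium.

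**What to change.** Amend Aim 3a as follows:

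1. Compute control completion from the attendance records of the program actually attended, obtained under the planned release for all randomized controls (R61 and R33), and from the EHR for the institution's own centers.
2. At the two-week contact and the month-3 call, both already planned, ask controls whether and where they attended PR.
3. Score controls who report no attendance as non-completers. This step is needed because most controls are expected not to complete, and someone who never attended has no records anywhere; without it, true non-completers would drift into the missing category.
4. Treat as missing only controls who report attending an outside program, or whose attendance is unknown, and whose records cannot be obtained. Report their number by arm.
5. Bound the primary result by scoring these controls first all as completers, then all as non-completers. For scale, 4 such controls among 72 move the control rate by at most 4/72 = 5.6 points.

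The cost is a few sentences, one added question, and record requests for those of the 75 planned controls who attend elsewhere. Some programs may not reply, and the observed difference may be smaller. Aim 3d has its calls made by a coordinator blinded to the intervention, so the month-3 question should come after the utilization items or be asked by someone else.
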